3.2 Exclusion Criteria

3.2.1 Patients must not have had chemotherapy ≤ 28 days or radiotherapy ≤ 7 days prior to study treatment.

NOTE: See section 4.6.1 for further clarification on palliative radiotherapy.

3.2.2 Patients who have not recovered to \leq Grade 1 or tolerable Grade 2 from adverse events due to agents administered ≥ 28 days earlier are not eligible.

3.2.3 Patient must not be a candidate for curative surgical or radiation therapy.
NOTE: Palliative radiotherapy is permitted.

3.2.4 Patients may not be receiving any other investigational agents \leq 28 days prior to study treatment.

3.2.5 Patients who have had prior exposure to immune checkpoint inhibitors are not eligible. Please contact principal investigator, for specific questions on potential interactions.
NOTE: Immune checkpoint inhibitors working through OX40 are an exception (for example, MEDI6383, MEDI6469, MEDI0562, oxelumab, and PF-04518600) and are permitted \geq 28 days prior to study registration.

3.2.6 Patients with active autoimmune disease or history of autoimmune disease that might recur, which may affect vital organ function or require immune suppressive treatment including chronic prolonged systemic corticosteroids (defined as corticosteroid use of duration one month or greater), should be excluded. These include but are not limited to patients with a history of:

- immune related neurologic disease
- multiple sclerosis
- autoimmune (demyelinating) neuropathy
- Guillain-Barre syndrome
- myasthenia gravis
- systemic autoimmune disease such as SLE
- connective tissue diseases
- scleroderma
- inflammatory bowel disease (IBD)
- Crohn's
- ulcerative colitis
- patients with a history of toxic epidermal necrolysis (TEN)
- Stevens-Johnson syndrome
- anti-phospholipid syndrome

NOTE: Subjects with vitiligo, type I diabetes mellitus, residual hypothyroidism due to autoimmune condition only requiring hormone replacement, psoriasis not requiring systemic treatment, or conditions not expected to recur in the absence of an external trigger are permitted to enroll.

3.2.7 Patients who have an uncontrolled intercurrent illness including, but not limited to any of the following, are not eligible:

- Ongoing or active infection (including minor localized infections) requiring oral or IV treatment

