4.3.1 Dose delays: Ipilimumab and/or nivolumab

Ipilimumab and/or nivolumab administration should be delayed for the following until resolution to \leq Grade 1 or baseline:

- Any Grade 2 non-skin, drug-related adverse event, except for fatigue and laboratory abnormalities
- Any Grade \geq 3 skin drug-related AE
- Any Grade \geq 3 drug-related laboratory abnormality with the following exceptions for lymphopenia, AST, ALT, or total bilirubin or asymptomatic amylase or lipase:
 - Grade 3 lymphopenia does not require a dose delay
 - If a participant has a baseline AST, ALT, or total bilirubin that is within normal limits, delay dosing for drug-related Grade 2 toxicity
 - If a participant has baseline AST, ALT, or total bilirubin within the Grade 1 toxicity range, delay dosing for drug-related Grade \geq 3 toxicity
 - Any Grade \geq 3 drug-related amylase or lipase abnormality that is not associated with symptoms or clinical manifestations of pancreatitis does not require dose delay.
- Any AE, laboratory abnormality or inter-current illness which, in the judgment of the investigator, warrants delaying the dose of study medication.

Participants that have drug-related toxicities that meet the criteria for dose delay, should have both drugs (ipilimumab and nivolumab) delayed until retreatment criteria are met. (Exceptions apply to the retreatment criteria after dose delay of ipilimumab and nivolumab for Grade \geq 3 amylase and lipase abnormalities that are not associated with symptoms or clinical manifestations of pancreatitis and that are attributed to ipilimumab alone.)

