4.3.2 Treatment discontinuation: Ipilimumab and/or nivolumab

Should the treating physician decide to discontinue treatment given suspicion for a drug-related side effect, the side effect should be attributed to one study drug to the best of the physician's ability. Either ipilimumab or nivolumab should be discontinued based on this attribution, or both if a definite attribution is not possible.

Ipilimumab and/or nivolumab should be discontinued permanently for the following:

- Any Grade 2 drug-related uveitis, eye pain, or blurred vision that does not respond to topical therapy and does not improve to Grade 1 severity within the re-treatment period OR requires systemic treatment
- Any Grade 3 non-skin, drug-related adverse event lasting > 7 days, with the following exceptions for laboratory abnormalities, drug-related uveitis, pneumonitis, bronchospasm, hypersensitivity reactions, infusion reactions, and endocrinopathies:
 - Grade 3 drug-related uveitis, pneumonitis, bronchospasm, hypersensitivity reaction, or infusion reaction **of any duration** (can be < 7 days) requires discontinuation
 - Grade 3 drug endocrinopathies adequately controlled with only physiologic hormone replacement do not require discontinuation
 - Grade 3 drug-related laboratory abnormalities do not require treatment discontinuation except:
 - Grade 3 drug-related thrombocytopenia > 7 days or associated with bleeding (aside from minor bleeds \leq Grade 1) requires discontinuation

NU Study Number: NU 16N03
BMS Study Number: CA 209-802

- Any drug-related liver function test (LFT) abnormality that meets the following criteria require discontinuation:
 - AST or ALT > 5-10 x ULN for > 2 weeks
 - AST or ALT > 10 xUL
 - Total bilirubin > 5 x ULN
 - Concurrent AST or ALT > 3 xULN and total bilirubin > 2 x ULN
- Any Grade 4 drug-related adverse event or laboratory abnormality, except for the following events which do not require discontinuation:
 - Grade 4 neutropenia < 7 days
 - Grade 4 lymphopenia or leukopenia
 - Isolated Grade 4 amylase or lipase abnormalities that are not associated with symptoms or clinical manifestations of pancreatitis. PI and Data Safety and Monitoring Committee (DSMC) should be consulted for Grade 4 amylase or lipase abnormalities.
 - Isolated Grade 4 electrolyte imbalances/abnormalities that are not associated with clinical sequelae and are corrected with supplementation/appropriate management within 72 hours of their onset

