Appendix D- Adverse Event Algorithms

Recommended management algorithms for suspected nivolumab related endocrinopathy, gastrointestinal toxicity, hepatotoxicity, neurologic toxicity, pulmonary toxicity, renal toxicity and skin toxicity

Endocrinopathy Management Algorithm

[figure not shown]
Rule out non-inflammatory causes. If non-inflammatory cause, treat accordingly and continue I-O therapy. Consider visual field testing, endocrinology consultation, and imaging.

Patients on IV steroids may be switched to an equivalent dose of oral corticosteroids (e.g. prednisone) at start of tapering or earlier, once sustained clinical improvement is observed. Lower bioavailability of oral corticosteroids should be taken into account when switching to the equivalent dose of oral corticosteroids.

GI Adverse Event Management Algorithm

[figure not shown]
Rule out non-inflammatory causes. If non-inflammatory cause is identified, treat accordingly and continue I-O therapy. Opiates/narcotics may mask symptoms of perforation. Infliximab should not be used in cases of perforation or sepsis.

Patients on IV steroids may be switched to an equivalent dose of oral corticosteroids (e.g. prednisone) at start of tapering or earlier, once sustained clinical improvement is observed. Lower bioavailability of oral corticosteroids should be taken into account when switching to the equivalent dose of oral corticosteroids.

Hepatic Adverse Event Management Algorithm

Rule out non-inflammatory causes. If non-inflammatory cause, treat accordingly and continue I-O therapy. Consider imaging for obstruction.

[figure not shown]
Patients on IV steroids may be switched to an equivalent dose of oral corticosteroids (e.g. prednisone) at start of tapering or earlier, once sustained clinical improvement is observed. Lower bioavailability of oral corticosteroids should be taken into account when switching to the equivalent dose of oral corticosteroids.

*I-O therapy may be delayed rather than discontinued if AST/ALT ≤ 8 x ULN or T.bili ≤ 5 x ULN.

**The recommended starting dose for grade 4 hepatitis is 2 mg/kg/day methylprednisolone IV.

Neurological Adverse Event Management Algorithm

[figure not shown]
Rule out non-inflammatory causes. If non-inflammatory cause, treat accordingly and continue I-O therapy.

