Patients on IV steroids may be switched to an equivalent dose of oral corticosteroids (e.g. prednisone) at start of tapering or earlier, once sustained clinical improvement is observed. Lower bioavailability of oral corticosteroids should be taken into account when switching to the equivalent dose of oral corticosteroids.

Pulmonary Adverse Event Management Algorithm

[figure not shown]
Rule out non-inflammatory causes. If non-inflammatory cause, treat accordingly and continue I-O therapy. Evaluate with imaging and pulmonary consultation.

Patients on IV steroids may be switched to an equivalent dose of oral corticosteroids (e.g. prednisone) at start of tapering or earlier, once sustained clinical improvement is observed. Lower bioavailability of oral corticosteroids should be taken into account when switching to the equivalent dose of oral corticosteroids.

Renal Adverse Event Management Algorithm

[figure not shown]
Rule out non-inflammatory causes. If non-inflammatory cause, treat accordingly and continue I-O therapy

Patients on IV steroids may be switched to an equivalent dose of oral corticosteroids (e.g. prednisone) at start of tapering or earlier, once sustained clinical improvement is observed. Lower bioavailability of oral corticosteroids should be taken into account when switching to the equivalent dose of oral corticosteroids.

Skin Adverse Event Management Algorithm

Rule out non-inflammatory causes. If non-inflammatory cause, treat accordingly and continue I-O therapy.

Patients on IV steroids may be switched to an equivalent dose of oral corticosteroids (e.g. prednisone) at start of tapering or earlier, once sustained clinical improvement is observed. Lower bioavailability of oral corticosteroids should be taken into account when switching to the equivalent dose of oral corticosteroids.

*Refer to NCI CTCAE v4 for term-specific grading criteria.

**If SJS/TEN is suspected, withhold I-O therapy and refer patient for specialized care for assessment and treatment. If SJS or TEN is diagnosed, permanently discontinue I-O therapy.

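### For Grade 3 SJS/TEN, Section 4.3 lists only a dose delay while the Appendix D skin footnote calls for a permanent stop, and no text says which governs

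*Combined protocol and SAP*

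**What the plan says.** Three current passages bear on the same event.

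- **Section 4.3.1 (dose delays).** It opens: "Ipilimumab and/or nivolumab administration should be delayed for the following until resolution to" Grade 1 or less, or baseline. One listed trigger is "Any Grade \geq 3 skin drug-related AE". The section adds that toxicity meeting the delay criteria holds both drugs until retreatment criteria are met. Its last item also allows a delay for any event at the investigator's judgment.
- **Section 4.3.2 (permanent discontinuation).** The Grade 3 item reads "Any Grade 3 non-skin, drug-related adverse event lasting > 7 days", followed by exceptions. A separate item covers any Grade 4 drug-related event, with listed exceptions. On which drug to stop, the section says: "Either ipilimumab or nivolumab should be discontinued based on this attribution, or both if a definite attribution is not possible".
- **Appendix D (Adverse Event Algorithms), skin footnote.** "If SJS/TEN is suspected, withhold I-O therapy and refer patient for specialized care for assessment and treatment". The next sentence is "If SJS or TEN is diagnosed, permanently discontinue I-O therapy". The appendix is introduced as "Recommended management algorithms for suspected nivolumab related endocrinopathy, gastrointestinal toxicity, hepatotoxicity, neurologic toxicity, pulmonary toxicity, renal toxicity and skin toxicity".

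**The concern.** Section 4.3 is where a treating site looks up when to hold and when to stop. For a Grade 3 case of SJS or TEN it leads to a hold that ends on recovery. The footnote at the back of the protocol leads to a permanent stop. The event is potentially life-threatening, and the protocol treats it as special by giving it its own footnote, yet Section 4.3 names neither SJS nor TEN.

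At stake is whether a patient who has recovered from a diagnosed case is dosed again and, where treatment is stopped, whether one of the two drugs may continue. Sites reading different parts of the same protocol could handle the same case differently.

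**Working it through.** No arithmetic applies: the point depends on no error rate, effect size or event count. The check sets the passages side by side for a drug-related, diagnosed case of SJS or TEN.

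| Grade | 4.3.1 | 4.3.2 | Appendix D skin footnote | Do they agree? |
|---|---|---|---|---|
| 3 | Delay both drugs until Grade 1 or less, or baseline | Grade 3 item is limited to non-skin events; a stop rests on judgment | Permanent stop | No |
| 4 | Also within the delay trigger (Grade 3 or higher) | Permanent stop; no skin event is among the exceptions | Permanent stop | On stopping, yes; on which drugs, unclear |

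**Grade 3: can another part of the protocol supply the stop?**

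1. *Hypersensitivity.* 4.3.2 stops Grade 3 hypersensitivity reactions of any duration, but that line sits under the non-skin item and does not name SJS or TEN.
2. *Long interruptions.* 4.3.2 stops treatment after an interruption of more than 6 weeks (42 days). It makes an exception for prolonged steroid tapers, with consultation of the principal investigator and the DSMC before restarting. A case that resolves sooner, or that falls under the taper exception, is not caught automatically.
3. *Investigator judgment in 4.3.2.* One item covers any adverse event that poses substantial clinical risk. It refers to continued nivolumab dosing only, and in the text available it appears among the exceptions to the interruption rule, so its level in the list is uncertain.
4. *Sections 4.7 and 4.9.* These allow treatment to end for unacceptable adverse events or toxicity without naming SJS or TEN.

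Items 3 and 4 allow a stop. Only the footnote calls for one.

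**Does Appendix D override Section 4.3?** Section 4.3 does not refer to it and no order of precedence is stated. The introduction presents the algorithms as recommendations for suspected nivolumab-related toxicity. It is therefore not plain that the footnote binds, or that it reaches an event attributed to ipilimumab, although 8.2.10 describes TEN as a known, labelled event in its account of ipilimumab safety.

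**Which drugs stop?** 4.3.2 stops the drug to which the event is attributed, and both where attribution is not definite. The footnote stops I-O therapy, a term the documents do not define. Where attribution is definite, 4.3.2 leaves the other drug available. Whether the footnote does so too cannot be read from the text.

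**The case against.** The strongest reply is that the texts can be followed together. 4.3.1 says when dosing must be held; it does not oblige anyone to resume. A site that holds under 4.3.1 and then stops under the footnote complies with both, and a specific rule for SJS/TEN can be read as supplementing a general rule for skin events. The recommended status of the appendix also counts against describing these as two binding rules in collision. This stands as far as it goes: a compatible reading exists. But the protocol does not state that reading, and a site that never leaves Section 4.3 is not led to it.

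Several stronger inferences are tempting, and the documents do not support them.

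- *That 4.3.2 exempts skin events, or that re-dosing after SJS is expressly permitted.* The Grade 3 item leaves skin events out by its scope, the Grade 4 item includes them, and no passage expressly allows re-dosing after SJS. The possibility follows from 4.3.1 together with the silence of 4.3.2.
- *That the texts also conflict below Grade 3.* 4.3.1 allows a delay at the investigator's judgment for any event. The Amendment 4 entry in the summary of changes, used here only to locate the footnote, places it on the Grade 3-4 branch of the skin algorithm. The flowchart itself was not available in the text reviewed, and the documents do not reproduce the CTCAE grades for SJS or TEN.
- *That the exclusion in 3.2.6, which lists "patients with a history of toxic epidermal necrolysis (TEN") and SJS, contradicts resumption on study.* It is an entry criterion and does not govern continuation.
- *That the interim accrual rule in 4.5 is materially affected.* With no event rate in the documents, this is speculation.
- *That 4.3.2 and the footnote flatly contradict each other on one drug or both.* 4.3.2 itself stops both when attribution is not definite, and I-O therapy is undefined. This is an ambiguity.

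**Conclusion.** The point holds in a narrow form. For a diagnosed, drug-related case of SJS or TEN graded 3, Section 4.3 provides a delay and leaves stopping to judgment, while the Appendix D footnote calls for a permanent stop, with no cross-reference and no rule of precedence. At Grade 4 the texts agree that treatment stops, and only the number of drugs is unclear.

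The frequency cannot be computed. The documents give no SJS/TEN rate, and the share of cases graded 3 depends on CTCAE definitions that they do not reproduce. The working assumption is that such events are rare. For each Grade 3 case the difference is resumption after recovery against permanent discontinuation.

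The conclusion rests on current protocol text only. It takes no view on which rule is clinically right. It merits correction because the consequence for an affected patient could be serious and the correction is small.

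**What to change.** In the next amendment, reconcile 4.3.1, 4.3.2 and the Appendix D skin footnote:

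1. Name SJS and TEN in 4.3.1 and 4.3.2, so that a diagnosed case has one stated action that matches the footnote.
2. State whether that action applies to nivolumab, ipilimumab or both, and define I-O therapy in the appendix.
3. Add a cross-reference from Section 4.3 to the algorithms and one sentence saying which text governs if they differ. Two appendices carry the letter D, so the reference should give the title.

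The action itself is for the sponsor and investigator to choose. The cost is a few lines of wording in three places and notice to sites. Sample size, endpoints, analysis and data collection do not change.

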Appendix D – Protocol Summary of Changes

Amendment 1 – February 16, 2017			
Approved by Scientific Review Committee: March 1, 2017			
Section(s) Affected	Prior Version	Amendment 1 Changes	Rationale
Cover Page; Study Summary	Title referred to treatment of “advanced” ACC and non ACC	Changes title to refer to treatment of “metastatic/recurrent” ACC and non ACC	Revised for consistency with population and eligibility criteria
Study Schema; Study Summary; 3.0 (Patient Eligibility); 3.1.2, 3.1.3 (Inclusion Criteria)	Patients “cannot be a candidate for surgical treatment”	Patients “cannot be a candidate for surgical or radiation treatment”	Revised for consistency with 3.2.3
Study Summary; 2.1 (Primary Objective); 6.2 (Primary Endpoint); 10.1.1 (Primary); 10.2 (Sample Size and Accrual)	“To assess progression-free survival rate (PFSR) at 6 months” or “To assess median progression-free survival rate (PFSR) as well as PFSR at 6 and 12 months”	To assess median progression-free survival (PFS) as well as PFS at 6 and 12 months	Progression-free survival does not need to be measured as a rate. To correct discrepancies – we will look at median and 12-month PFS as well as 6-month.
3.1.3 (Inclusion Criteria)	“Patients must have received at least one prior line of systemic therapy”	“Patients may or may not have received prior therapy for their recurrent/metastatic disease ”	Disease team requested to expand eligibility to patients who have not received treatment for metastatic/recurrent disease.
4.1 (Overview); 4.2 (Treatment Administration); 4.2.1 (Nivolumab); 4.2.2 (Ipilimumab)	Treatment windows were as follows: Nivolumab over 30 mins (± 5 mins) / 60 mins (± 10 mins) Ipilimumab over 90 mins (± 5 mins)	Changes treatment windows: Nivolumab over 30 mins (-5 / $+15$ mins) / 60 mins (-10 / $+15$ mins) Ipilimumab over 90 mins (-5 / $+15$ mins)	Allows for flexibility of a longer infusion if needed, without compromising safety
11.6.2 (Other Protocol Deviations)	Refers to “Promptly Reportable Non-Compliance (PRNC)”	Changes to “Reportable New Information (RNI)”	Administrative – to align with current internal policies
Amendment 2 – March 13, 2017			
Approved by Scientific Review Committee: March 27, 2017			
Section(s) Affected	Prior Version	Amendment 2 Changes	Rationale
1.4 (Exploratory Studies); 2.3.3 (Exploratory Objectives & Endpoints); 5.0 (Study Procedures); 9.0 (Correlatives / Special Studies)	Included cfDNA exploratory objective and correlative samples, to be performed at Guardant	Removes cfDNA samples and any reference to such analysis at Guardant. Such samples will be collected and sent as part of SOC, and have been added as a separate procedure in 5.0.	Administrative decision to remove samples due to logistical issues with Guardant
5.0 (Study Procedures)	n/a	Adds optional Echo/ECG at baseline for patients with a history of congestive heart failure or at risk because of	Response to CTEP action letter advising for cardiac monitoring as a result of recent myocarditis

NU Study Number: NU 16N03
BMS Study Number: CA 209-802

		underlying cardiovascular disease	
5.0 (Study Procedures, #12); 9.0 (Correlative/ Special Studies)	Tissue was to be collected from SOC biopsies throughout the study "If the patient agrees", and were not mentioned in 9.0	Removes "If the patient agrees" and adds "if feasible"	Tissue collection from SOC biopsies will be mandatory if feasible, and the patient's overall consent will account for this
5.0 (Study Procedures); 9.0 (Correlative/ Special Studies)	NGS was listed as a correlative sample	Adds NGS as a separate study procedure, which will be performed as part of standard of care (rather than a correlative sample)	Clarification – NGS is performed SOC and is not meant to be processed through Pathcore or as a research charge.
5.0 (Study Procedures, #11)	n/a	Adds blood volume and tube types for correlative samples.	Clarification

Amendment 3 – May 17, 2017*Approved by Scientific Review Committee: June 2, 2017*

Section(s) Affected	Prior Version	Amendment 3 Changes	Rationale
Cover Page	Includes [name] as Sub-Investigator	Removes [name] as Sub-Investigator	Administrative; [name] has left the university
Study Summary; 6.3 (Secondary Endpoints)	Secondary objective to look at clinical benefit rate (CBR) at 24 weeks	Changes secondary objective to clinical benefit rate (CBR) and 6 and 12 months	Revision of discrepancy
Study Summary; 2.2.2 (Secondary Objectives & Endpoints); 6.7 (Immune-related RECIST); 10.1.2 (Secondary)	Secondary objective of efficacy using immune-related response criteria (irRC)	Changes secondary objective to efficacy using immune-related RECIST (irRECIST). Updates criteria in 6.7 to align with current definitions of irRECIST	Revision of discrepancy; irRECIST is most current immune-related response criteria
3.1.9 (Inclusion Criteria); 5.0 (Study Procedures, #8)	Pregnancy test was required within 72 hours of Registration	Pregnancy test required ≤14 days prior to registration	Clarification to allow for greater flexibility in screening
3.2.1, 3.2.4, 3.2.13 (Exclusion Criteria); 4.6.2 (Prohibited Medications)	Windows for prohibited medications were from study registration	Windows for prohibited medications are changed to be measured from start of study treatment	A window from study treatment rather than registration allows for greater flexibility at screening, and is more clinically appropriate, per PI
4.2.2. (Ipilimumab); 5.0 (Study Procedures, #10)	n/a	Adds: "Dosing will be based on weight at baseline, however if there is a weight change $\geq 10\%$, the dose should be adjusted accordingly"	Clarification
5.0 (Study Procedures)	TSH	TSH with reflex	Clarification
	#2: Vital signs included pulse, respirations, and blood pressure	#2: Removes respirations from vital signs	Missing respirations are a common source for protocol deviations; they are not clinically necessary
	#11: Correlative blood samples were to be collected in 10mL heparin tubes	#11: Changes correlative tubes to 8mL heparin tubes	Correction

Amendment 4 – August 14, 2017

Approved by Scientific Review Committee:			
Section(s) Affected	Prior Version	Amendment 4 Changes	Rationale
Cover Page; Study Summary	Title: Phase II study of nivolumab and ipilimumab for treatment of metastatic/recurrent adenoid cystic carcinoma and non-adenoid cystic carcinoma	Title: Phase II study of nivolumab and ipilimumab for treatment of metastatic/recurrent adenoid cystic carcinoma of all anatomic sites of origin and non-adenoid cystic carcinoma malignant tumors of the salivary gland	Clarification to address discrepancies in study population
Study Schema; 3.1.1 (Inclusion Criteria);	Study population was to include ACC patients with evidence of disease progression.	Clarifies that ACC can be of any anatomic site of origin	Clarification of study population to ensure it is inclusive
Study Schema; 3.1.2, 3.1.3 (Inclusion Criteria); 3.2.3 (Exclusion Criteria)	Study population was to include ACC patients who are not surgical or radiation candidates	Clarifies that patients cannot be a candidate for curative surgical or radiation therapy	Clarification; distinguishes between surgical/radiation therapy which is palliative or otherwise non-curative, which is permitted
3.1.3 (Inclusion Criteria)	NOTE: There is no limit to the number of prior therapies for stage IV Disease	NOTE: There is no limit to the number of prior systemic therapies	Clarification
3.1.4 (Inclusion Criteria)	n/a	Adds note that scans must be \leq 28 days prior to study treatment	Clarification
3.1.7 (Inclusion Criteria)	Requirements for bilirubin and creatinine were listed as $<3.0 \times \text{ULN}$ and $> 30 \text{ mL/minute}$	Updates to \leq and \geq respectively	Clarification; criteria are meant to be inclusive of the borderline value
3.2.1 (Exclusion Criteria)	Chemotherapy and radiotherapy were not permitted \leq 28 days prior to study treatment	Shortens window for radiotherapy; now permitted >7 days prior to study treatment	Allows greater flexibility in the allowance for radiotherapy since it might be clinically indicated to have radiotherapy close to treatment and is lower risk
3.2.5 (Exclusion Criteria)	Included a reference to specific PD-1, PD-L1, and CTLA4 monoclonal antibodies	Removes reference and list of specific monoclonal antibodies	The list is incomplete and potentially misleading. The PI can be contacted for any questions on specific immune checkpoint inhibitors
3.2.12 (Exclusion Criteria)	Patients were excluded with any known positive test for Hepatitis B or C indicating acute or chronic infection	Only acute, and not chronic, Hepatitis B or C infection is considered exclusionary	A controlled chronic condition does not indicate the need to exclusion
4.3.2 (Treatment Discontinuation); 4.7 (Duration of Therapy); 7.4.1	Referred to NU's internal Data Monitoring Committee (DMC)	Changes to Data Safety Monitoring Committee (DSMC)	To align with updated policies

NU Study Number: NU 16N03
BMS Study Number: CA 209-802

(Routine Reporting); 7.4.3.1 (Reporting to NU QAM/DSMC); 11.9 (Publication Policy)			
5.0 (Study Procedures)	Window for treatment and procedures was ± 4 days	Changes treatment and procedure window to $-2/+4$ days Changes EOT window to ± 7 days	Nivolumab cannot be given <12 or 24 days after the previous dose; smaller window prevents overlap Larger EOT window allows flexibility
5.0 (Study Procedures #1,3)	Baseline imaging was to include CT of Neck, Chest, Abdomen and Pelvis within 28 days prior to registration.	Baseline imaging must be within 28 days prior to starting treatment and may include Neck, Chest, Abdomen and Pelvis (or any combination) at investigator discretion.	Allows more flexibility for investigator to use discretion as to which scans are clinically relevant. The timing of scans from treatment is more important to get the most accurate picture of disease burden.
5.0 (Study Procedures #3,4,5)	One footnote was included with all instructions related to scans on study	Separates into 3 footnotes to clearly delineate instructions for scans at baseline, prior to each cycle, and in the case of PD. Re-numbers subsequent footnotes appropriately.	Simplified for clarity
5.0 (Study Procedures, #20)	NGS was to be performed using Foundation One, "any time prior to study treatment, preferably within 6 weeks"	
 • Removes Foundation One • NGS can be performed any time prior to study treatment as long as the patient has not received other treatment since the biopsy. • Clarifies that tissue should be taken from the lesion demonstrating progression and that patients may agree to provide a fresh biopsy if not available 	
 • Allows greater flexibility in using different companies for NGS testing • Clarification; it is more important that the biopsy not be intervened by treatment rather than the actual timing • Clarification
5.0 (Study Procedures, #21)	A liquid biopsy was to be performed prior to study treatment, "preferably within 6 weeks, per clinician's discretion"	Liquid biopsy can be performed any time prior to study treatment "as long as the patient has not received other treatment since the biopsy, per standard of care procedures"	Clarification; it is more important that the sample not be intervened by treatment rather than the actual timing
8.1 (Nivolumab)	Contained outdated language on nivolumab details. Specifically: 8.1.4: Nivolumab could be stored up to 4 hours at room temperature 8.1.6: Listed details on minimum concentration with weight-based dosing	Updates nivolumab details to align with new Investigator's Brochure and internal template language for nivolumab protocols. Specifically: 8.1.4: Nivolumab can be stored up to 8 hours at room temperature	Updated for simplicity to align with other internal nivolumab protocols

NU Study Number: NU 16N03
BMS Study Number: CA 209-802

		8.1.6: Removes reference to weight-based dosing preparation	
Amendment 4 continued – September 8th, 2017			
Approved by Scientific Review Committee:			
Section(s) Affected	Prior Version	Amendment 4 Changes cont.	Rationale
7.3 (Reporting of pregnancy and lactation); Appendix A	Contraception timing post-treatment was not specified; pregnancy was to be monitored up to at least 6 half-lives after product administration	WOCBP will be instructed to adhere to contraception for a period of 5 months after the last dose of nivolumab. Men receiving nivolumab will be instructed to adhere to contraception for a period of 7 months after the last dose of nivolumab.	Updated per BMS to align with new nivolumab IB v16 requirements for pregnancy and contraception.
8.1.9 (Availability and Supply)	Did not specify timing for drug re-supply requests	Drug re-supply should be submitted 10 business days before the delivery date	Updated for accuracy per BMS
8.1.12, 8.2.12 (Return & Retention of Study Drug)	n/a	Adds statement: "Inform BMS on all drug destructions pertaining to both nivolumab and ipilimumab."	BMS request.
Tale 8.1 (Nivolumab Product Description)	5-10 vials per carton were supplied	5 vials per carton are supplied	Updated for accuracy per BMS
8.2.4 (Storage and stability)	n/a	Replaces language with internal ipilimumab template	For consistency among internal IIT protocols using ipilimumab
Table 8.2 (Ipilimumab Product Description)	4 vials per carton were supplied	5 vials per carton are supplied	Updated for accuracy per BMS
Appendix B	
Contained outdated AE Management Algorithms. Specific outdated parameters include:
 
Hepatic:
 
 • Discontinue for AST/ALT >5xULN and/or Tbili >3xULN 
Pulmonary (G3-4):
 
 • Includes example immunosuppression 
Renal (G2-3):
 
 • “Consider renal biopsy” 
Skin (G3-4):
 
 • n/a 	
Updates AE Management Algorithms to align with nivolumab IB v16. Specific changes to AE management include:
 
Hepatic:
 
 • Discontinue for AST/ALT > 5xULN or Tbili > 3xULN 
Pulmonary (G3-4):
 
 • Removes examples of immunosuppression 
Renal (G2-3):
 
 • “Consider renal biopsy with nephrology consult” 
Skin (G3-4):
 
 • Adds footnote: “If SJS/TEN is suspected, withhold I-O therapy and refer patient for specialized care for assessment and treatment. If SJS or TEN is diagnosed, 	Updated per BMS for consistency with new nivolumab IB v16 and additional or clarified safety measures.

NU Study Number: NU 16N03
BMS Study Number: CA 209-802

		permanently discontinue I-O therapy.”	
Amendment 5 – September 11th 2019			
Section(s) Affected	Prior Version	Amendment 5 Changes	Rationale
Coverpage 3.0 (Subject Eligibility)	Lists [name] as the PI for the study	Changes to list [name] as the PI	Change due to original PI leaving Northwestern
Amendment 6 – October 11th 2019			
Section(s) Affected	Prior Version	Amendment 6 Changes	Rationale
4.6.1 (Permitted Medications) 4.6.2 (Prohibited Medications)	n/a	Adds guidelines of permitted palliative radiation or surgery on study	To allow patients to have palliative radiation or surgery when on treatment
Amendment 7 – June 26th 2020			
Section(s) Affected	Prior Version	Amendment 7 Changes	Rationale
Coverpage	Lists [name] as the PI for the study	Changes to list [name] as the PI	Change due to PI leaving Northwestern
	Lists Sub-investigators for the study	Removes Sub-investigators from the coverpage	Per new policies, sub-investigator lists will be maintained in DOA and APL only and not on the protocol coverpage
3.0 (Subject Eligibility) 9.1 (Specimen Banking)	Lists the PIs by name and in some places provides contact information	Removed or replaced with “PI”	Removed as PI is leaving Northwestern and to provide consistency throughout the protocol
Amendment 8			
Section(s) Affected	Prior Version	Amendment 8 Changes	Rationale
8.2.5 Ipilimumab storage and stability	Previous information	Updated with current information	As mandated by BMS, based on current IB
8.2.6 Preparation of ipilimumab	Previous information	Updated with current information	As mandated by BMS, based on current IB
8.2.9 Availability and supply of Ipilimumab And 8.2.12 Return and retention of drug	Previous information	Updated to state, “Starting January 2023, Ipilimumab will be supplied in 50mg vials. Each carton will contain 6 x 50mg vials.” Other associated information updated	As mandated by BMS, based on current IB
